5.3.3.2. Estimator (Analysis) for the Supplementary Estimands of the Primary Endpoint

5.3.3.2.1. All ICEs Composite

The same estimator used for the primary estimand will be used for the supplementary estimand, with the exception that the treatment policy no longer applies to ICE5 and ICE6, as all ICEs are addressed by the composite strategy. After accounting for the ICE strategies, participants whose endoscopic recurrence status is missing for the primary endpoint will be considered to having endoscopic recurrence.

5.3.4. Subgroup Analyses

To evaluate the consistency of the primary analyses, subgroup analyses based on demographics (eg, age, sex, race, body weight, region), baseline characteristics (CD duration, involved gastrointestinal areas, number of CD related prior surgeries, CDAI score), baseline CD-related concomitant medication usage and biologic history (oral corticosteroids, oral 5-ASA compounds, immunomodulators(6-MP, AZA, or MTX), oral corticosteroids and immunomodulators, oral corticosteroids or immunomodulators prior biologic use), and potential risk factors for recurrence of active CD (number of risk factors for recurrence of active CD, the qualifying surgery was the patient's second intra-abdominal operation for CD in the past 10 years, the qualifying surgery was the patient's third (or more) intra-abdominal operation for CD, the qualifying surgery was performed for a penetrating complication of CD (ie, an intra-abdominal abscess, internal fistula, sinus tracts or intestinal perforation), the patient has any history of perianal fistulizing CD provided that this has not been active in the 3 months prior to study start, the patient is a cigarette smoker), the patient has Kono-S (antimesenteric functional end-to-end handsewn), the patient has mesenterectomy will be performed if sufficient data are available in the subgroup.

For subgroup analyses, the analysis sets are based on the **FAS**. Subgroup analyses will be performed when the number of participants in each subgroup permits. The following subgroup analyses will be performed:

- Statistical Analysis Plan CNTO1959CRD3007
- 1. The consistency of treatment effect for the primary endpoint will be evaluated for the subgroups defined in Section 5.8.5, using the **primary estimand**:

For each of the subgroups identified in Section 5.8.5, the rate (risk) difference of guselkumab vs placebo group and the associated p-values and 95% confidence intervals will be provided using forest plots. The difference in proportions, p-values and confidence intervals will be provided based on the same model specified in Section 5.3.3.1.

2. Using the primary estimand, an analysis of the primary endpoint will be performed for each region, country, and investigator site. This analysis will be descriptive and statistical testing will not be applied.

5.3.5. Sensitivity Analyses

The following sensitivity analyses will be based on varying assumptions of the missing data, and different definition for the primary endpoint of endoscopic recurrence.

5.3.5.1. Tipping Point Analysis

Tipping point sensitivity analyses will be conducted to explore the potential impact of missing data and to show the robustness of the conclusion based on the primary analysis. The analysis finds a (tipping) point in this spectrum of assumptions, at which conclusions change from being favorable to the experimental intervention to being unfavorable. After such a tipping point is determined, clinical judgment can be applied as to the plausibility of the assumptions underlying this tipping point. The tipping point can be identified when the result is no longer statistically significant.

The Tipping Point Analysis will be applied to primary endpoint and will use the primary estimand, after accounting for ICEs. For participants with missing data for the endpoint, the endoscopic recurrence (recurrence/no recurrence) will be imputed in an increasing manner by participant level for each intervention group. Specifically, for each participant, a recurrence/no recurrence status will be imputed starting with the scenario where all participants have recurrence up to the scenario where all participants have no recurrence. This would include all possible scenarios of recurrence status for all missing data allowing assumptions about the missing outcomes to vary independently, including scenarios where participants randomized to the Guselkumab group have worse outcomes than participants on placebo. For each scenario, the adjusted intervention difference (with CMH weight) in proportion of participants achieving the primary endpoint between the Guselkumab group and placebo group and the corresponding p-values will be provided.

5.3.5.2. Modified Endoscopic Recurrence

This sensitivity analysis will evaluate the primary endpoint in a similar fashion. Same ICE strategy and similar estimand and estimators will be used, with exception that

- The definition of endoscopic recurrence: endoscopic recurrence prior to or at Week 48 as defined by modified Rutgeerts score i2b or above in the neo-terminal ileum, anastomotic site, or its equivalent elsewhere in the GI tract (eg, colonic ulceration).
- Variable (endpoint): A binary recurrence variable (recurrence/no recurrence) where recurrence is defined as Endoscopic Recurrence prior to or at Week 48 (as defined by modified Rutgeerts score greater than i3) or experiencing intercurrent events (ICEs) 1-4.

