9.4.4. Other/Exploratory Endpoints

The other/exploratory endpoints include but are not limited to the endpoints described in Section 3. A complete list of the other endpoints will be provided in the SAP. The testing of these endpoints will not be controlled for multiplicity and nominal p-values will be provided.

Other endpoints include:

- Change in PROMIS-Fatigue Short Form 7a score over 48 weeks
- Abdominal pain (AP score = 0) at each post baseline visit through Week 152
- Time to a flare of abdominal pain
- Clinical remission (CDAI <150) at each post baseline visit
- Change in PROMIS-Fatigue SF 7a at each post baseline visit through Week 152
- Change in PROMIS-29 score, both overall score and individual domain scores at each post baseline visit through Week 152
- Change from baseline in the WPAI at each post baseline visit through Week 152
- The number of participants not on corticosteroids and without disease recurrence at each post baseline visit through Week 152
- The number of participants not on corticosteroids and without endoscopic or disease recurrence at each post baseline visit through Week 152
- Endoscopic recurrence prior to or at Week 24
- Histologic score (as measured by Geboes scale/RHI/GHAS) at Week 48 ileocolonoscopy
- The number of participants with Geboes score over 3.1 at Week 48 ileocolonoscopy

- The number of participants with Geboes score of 2.0 or less at Week 48 ileocolonoscopy
- Clinical remission (CDAI <150) at Week 24 after initiation of guselkumab SC induction
- Clinical response (CDAI decrease of <100 points or CDAI <150) 24 weeks after initiation of guselkumab SC induction
- Disease recurrence (using definition described in Section 9.4.3) at Week 152
- Fecal calprotectin recurrence, defined by calprotectin of >200 μg/g with a 100 μg/g increase over baseline
- The change from baseline in fecal calprotectin concentration at all postbaseline visits through Week 152
- The change from baseline in CRP concentration at all postbaseline visits through Week 152

An additional exploratory analysis for risk factors of endoscopic and disease recurrence will be performed. A sensitivity analysis of the primary endpoint will be performed using a Rutgeerts score of > i3 as the definition for endoscopic recurrence.

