5.3. Primary Endpoint(s) Analysis

5.3.1. Definition of Endpoint

The primary endpoint is endoscopic recurrence prior to or at Week 48 as defined by modified Rutgeerts score \geq i2a in the neo-terminal ileum, anastomotic site, or its equivalent elsewhere in the GI tract (eg, colonic ulceration).

Rutgeerts score

Score	Endoscopic Findings
i0	No lesions
i1	< 5 aphthous lesions
i2	> 5 aphthous lesions with normal mucosa between the lesions or skip areas of larger lesions or lesions confined to the ileocolonic anastomosis (ie, < 1 cm in length)
i2a	Lesions confined to the ileocolonic anastomosis (including anastomotic stenosis)
i2b	More than 5 aphthous ulcers or larger lesions, with normal mucosa in-between, in the neoterminal ileum (with or without anastomotic lesions)
i3	Diffuse aphthous ileitis with diffusely inflamed mucosa
i4	Large ulcers with diffuse mucosal inflammation or nodules or stenosis in the neoterminal ileum

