5.3.2. Estimand

5.3.2.1. Primary Estimand

An estimand is a precise definition of the primary targeted treatment effect defined by the following 5 attributes: Study Intervention, population, variable (endpoint), intercurrent events (ICEs) and corresponding strategies, and population-level summary.

Primary Trial Objective: To evaluate the efficacy of guselkumab treatment prior to or at Week 48 compared with placebo in preventing endoscopic recurrence of CD in participants after surgery.

Estimand Scientific Question of Interest: What is the proportion of participants developing endoscopic recurrence prior to or at Week 48, and thus considered to have benefited from guselkumab versus placebo?

Study intervention:

- Experimental: Guselkumab ^{CCI} at Week 0 and then ^{CCI} at Week 8, then ^{CCI} thereafter through the end of the total study period.
- Control: Matched placebo CCI at Weeks 0 and 8 and then CCI thereafter through the end of the total study period.

Population: Participants with recent (<49 days) qualifying surgery and no evidence of active Crohn's disease postoperatively.

Variable: A binary recurrence variable (recurrence/no recurrence) where recurrence is defined as Endoscopic Recurrence prior to or at Week 48 (as defined by modified Rutgeerts score greater than or equal to i2a in the neo-terminal ileum, anastomotic site, or its equivalent elsewhere in the GI tract (eg, colonic ulceration)) or experiencing intercurrent events (ICEs) 1-4 presented below.

Summary Measure (Population-level summary): Difference in proportions of the binary recurrence variable of endoscopic recurrence, as described above, between guselkumab group and the placebo group.

Intercurrent events and their corresponding strategies:

The ICEs considered for this study are listed in Table 7:

Table 7:	Intercurrent Events and Corresponding Analysis Strategies for Endoscopic Recurrence prior to
	or at Week 48

Inte	ercurrent Events (between baseline and Week 48)	Analysis Strategy for Intercurrent Events
1. 2.	A CD-related surgery (with the exception of minor procedures such as drainage of a superficial abscess or seton placement, etc.) A prohibited change in CD medication	
3. 4.	Discontinuation of study intervention due to lack of efficacy or an AE of worsening CD Cross over to open-label guselkumab	

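### SAP 5.3.5.2 sets two incompatible Rutgeerts thresholds for one sensitivity analysis of the primary endpoint, and neither clearly matches Protocol 9.4.4

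*SAP*

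**What the plan says.** The primary variable in SAP 5.3.2.1 is inclusive and written out in words: "as defined by modified Rutgeerts score greater than or equal to i2a in the neo-terminal ileum", with intercurrent events (ICEs) 1-4 also counted as recurrence.

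SAP 5.3.5.2 repeats this analysis with a changed endoscopic definition, given in two bullets:

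- Definition bullet: "modified Rutgeerts score i2b or above in the neo-terminal ileum, anastomotic site", or the equivalent elsewhere in the GI tract.
- Variable bullet: recurrence "as defined by modified Rutgeerts score greater than i3" "or experiencing intercurrent events (ICEs) 1-4".

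The scale in SAP 5.3.1 runs i0, i1, i2 (divided into i2a and i2b), i3, i4. The only grade above i3 is i4: "Large ulcers with diffuse mucosal inflammation or nodules or stenosis in the neoterminal ileum".

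Protocol 9.4.4 announces the analysis: "A sensitivity analysis of the primary endpoint will be performed using a Rutgeerts score of" a stated grade, namely "i3 as the definition for endoscopic recurrence". In the text available for review the sign before i3 is a strict greater-than. That may be a greater-than-or-equal sign that lost its bar in conversion from PDF. The protocol's summary of changes describes the same addition with an inclusive i3 threshold.

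SAP Appendix 2, the place for changes to protocol-planned analyses, shows no entry on this in the public text.

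**The concern.** The two bullets describe one analysis and cannot both be programmed. One counts three grades as endoscopic recurrence and the other, as worded, counts one. The protocol offers a third possibility, i3 or above, which counts two.

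This is the only planned sensitivity analysis of the primary endpoint that moves the endoscopic threshold. The tipping point analysis in SAP 5.3.5.1 varies only the missing outcomes. The three thresholds answer different questions: i2b or above drops lesions confined to the anastomosis, i3 or above looks at diffuse disease, and i4 looks at the most severe grade. If the text is not settled before unblinding, the threshold could be chosen after the results are known. The number of events, and so what the analysis can show, also differs between the readings.

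**Working it through.** **Step 1. Grades counted in the endoscopic component (scale in SAP 5.3.1).**

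| Source | Threshold | Grades counted |
|---|---|---|
| SAP 5.3.2.1, primary | i2a or above | i2a, i2b, i3, i4 |
| SAP 5.3.5.2, definition bullet | i2b or above | i2b, i3, i4 |
| Protocol 9.4.4, if inclusive | i3 or above | i3, i4 |
| SAP 5.3.5.2, variable bullet, literal | greater than i3 | i4 |

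A lost symbol cannot explain the variable bullet, because the threshold is in words. The SAP also writes an inclusive threshold in words for the primary variable. Even if i3 or above was meant, it still differs from i2b or above.

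**Step 2. Inputs for the size (SAP Section 3).** 185 per arm, two-sided alpha 0.05, recurrence 50% on placebo and 30% on guselkumab at i2a or above. Relative risk 30/50 = 0.6.

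**Step 3. Formula, checked on the plan's own figure.** Two-proportion power with pooled variance under the null and no continuity correction:

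power = Φ[(d − 1.96·s0)/s1], where d = p1 − p2, s0 = √(2·p̄(1−p̄)/n), s1 = √((p1(1−p1) + p2(1−p2))/n), p̄ = (p1+p2)/2.

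For 50% v 30%: d = 0.20, s0 = 0.0509, s1 = 0.0499, so z = 2.009 and power is 97.8%. The SAP states 97.7%, so the method reproduces it.

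**Step 4. Stricter thresholds.** The documents give no grade distribution and no power for this analysis. Three assumptions are therefore needed:

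- recurrences split evenly over i2a, i2b, i3 and i4;
- the relative risk of 0.6 holds at every threshold;
- no event enters only through an ICE.

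With f the share of recurrences that meet the threshold, the rates are 50%·f and 30%·f.

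| Threshold | f | Placebo v guselkumab | Power |
|---|---|---|---|
| i2b or above | 0.75 | 37.5% v 22.5% | 89% |
| i3 or above | 0.50 | 25% v 15% | 67% |
| i4 only | 0.25 | 12.5% v 7.5% | 36% |

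**Step 5. Let ICEs contribute.** Suppose 20% of the recurrences that miss the stricter grade still count through ICEs 1-4. Then f becomes f + 0.2·(1 − f).

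| Threshold | f | Placebo v guselkumab | Power |
|---|---|---|---|
| i2b or above | 0.75 + 0.2·0.25 = 0.80 | 40% v 24% | 91% |
| i3 or above | 0.50 + 0.2·0.50 = 0.60 | 30% v 18% | 77% |
| i4 only | 0.25 + 0.2·0.75 = 0.40 | 20% v 12% | 56% |

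The gap between the two SAP bullets narrows from 53 points (89 − 36) to 35 points (91 − 56) but does not close.

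**Step 6. Other grade splits, without ICEs.** Power is 91% at f = 0.8, 77% at 0.6, 56% at 0.4, 29% at 0.2 and 16% at 0.1.

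**The case against.** A reader might infer more than the documents support, in four ways.

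*That the analysis would test i4 lesions only.* This is the literal reading of the endoscopic part of one bullet, not of the binary variable. ICEs 1-4 count whatever the grade. ICE 4 is cross over to open-label guselkumab, which under Protocol 6.5.1 can follow a centrally confirmed score of i2a or above at the optional Week 24 examination. Nor does the protocol's sign prove an i4-only intent, since it may be a conversion loss. An inclusive i3 threshold is a plausible intent, and it lies between the two extremes.

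*That the purpose is to isolate anastomotic-only lesions.* No passage says so. SAP 5.3.5 speaks only of a different endpoint definition, and Protocol 9.4.4 gives no rationale. Protocol 8.1.3 notes that i2 outcomes have been mixed, but also that recent studies found no difference in clinical recurrence between i2a and i2b. A check on more severe recurrence fits the text equally well.

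*That i2b or above must therefore be the right threshold.* The protocol and the SAP variable bullet both refer to i3. Only the definition bullet says i2b.

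*That a positive primary result would be put at risk.* Under SAP 5.3.3.1 success rests on the primary test alone. This analysis is not in the testing sequence of SAP 5.4.1.3 and no power is claimed for it, so low power here is not a design error.

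These points limit the concern. They do not remove the mismatch: two thresholds stand in one subsection and no text reconciles them.

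**Conclusion.** The concern holds as an inconsistency of definition. SAP 5.3.5.2 cannot be carried out as written, because its bullets count different grades and neither clearly matches the i3 analysis in Protocol 9.4.4.

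The 89%, 67% and 36% are illustrations that rest on the Step 4 assumptions. They show that the choice matters; they do not predict what the trial would have found.

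Severity is minor. Besides lying outside the testing hierarchy, the analysis will not be run as planned: the SAP introduction says that the study was discontinued for business reasons with four subjects enrolled, and that the planned analyses are kept for reference. No reported result changes. The text matters as the plan of record and if it is reused.

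**What to change.** State one inclusive threshold in both bullets of SAP 5.3.5.2 and remove the strict wording in the variable bullet. There are two consistent ways to do this, and the sponsor should say which is meant:

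1. Use i3 or above in both bullets, to match the protocol's i3 analysis.
2. If the aim is to exclude anastomotic-only i2a lesions, use i2b or above in both bullets, record the departure from Protocol 9.4.4 in SAP Appendix 2, and list i3 or above as a separate analysis.

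In either case, confirm that the sign in Protocol 9.4.4 is inclusive. The cost is one or two wording edits and, for the second option, one Appendix 2 entry and at most one extra sensitivity table.

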5.4. Secondary Endpoint(s) Analysis

5.4.1. Key Confirmatory Secondary Endpoint(s)

The following are the first secondary endpoint and second secondary endpoint:

- Clinical remission without disease recurrence at Week 48
- Time to disease recurrence

The analyses of the first secondary endpoint will be performed after the test of the primary endpoint. The analyses of second secondary endpoint will be performed after the test of the primary endpoint and the first secondary endpoint.

5.4.1.1. Definition of Endpoint(s)

Clinical remission without disease recurrence is a composite endpoint defined by the following:

- CDAI < 150 at Week 48 and
- No endoscopic recurrence as defined by Rutgeerts score < i2a by Week 48 and
- Have not experienced a disease recurrence as defined below

Disease recurrence is a composite endpoint defined by the following:

- A ≥ 70-point increase from baseline in CDAI score at beyond 8 weeks after randomization; and a CDAI score of ≥ 200 **and** evidence of endoscopic recurrence. Endoscopic recurrence is defined as a modified Rutgeerts score of ≥ i2a at the anastomotic site or its equivalent elsewhere in the GI tract, unless a stool test for C. difficile toxin or other enteric pathogen is positive
- In event of a positive test for enteric pathogen including C. difficile toxin, the underlying infection should be treated and if ileocolonoscopy has not yet been performed, it should only be done when the infection has resolved, and if disease recurrence threshold is still met
- OR initiation of a physician-prescribed corticosteroids, or an increase in the dose of steroids already being taken (by greater than 5 mg/day), for over one week for the treatment of CD and evidence of endoscopic recurrence as described above, unless a stool test for C. difficile toxin or other enteric pathogen is positive
- OR a new draining external fistula
- OR the reopening and draining of a previously existing external fistula
- OR developing a new internal fistula
- OR developing a new perianal abscess
- OR developing a new intra-abdominal abscess more than three months after the date of the index surgery

Participants who have confirmed endoscopic recurrence without disease recurrence at Week 24 or Week 48 and cross over to open-label guselkumab treatment will be censored at cross over for the time to disease recurrence endpoint.

Abdominal pain free at Week 48 is defined as abdominal pain (AP) score = 0 at Week 48

Time-to-recurrence of symptoms is defined as time to attaining an AP mean daily score >1 (and also >1 point higher than baseline) along with stool frequency (SF) mean daily score >3 (and also >3 higher per day than baseline) for 2 consecutive weeks through Week 48. Participants who cross over to open-label guselkumab treatment and do not have recurrence of symptoms will be censored at cross over for the time to recurrence of symptoms endpoint.

Steroid free clinical remission at Week 48 is defined as CDAI <150 and no corticosteroids within 30 days.

